8.3. Data Presentation Description

The following decimal description will be used for the demography, reactogenicity, immunogenicity, and persistence analyses.

Display Table	Parameters	Number of Decimal Digits
Demographic characteristics	Mean, median age	1
Demographic characteristics	SD (age)	1
rSBA-MenA	GMT	1
rSBA-MenC	GMT	1
rSBA-MenW-135	GMT	1

MenACWY-TT-100 (C0921004)

Display Table	Parameters	Number of Decimal Digits
rSBA-MenY	GMT	1
hSBA-MenA	GMT	1
hSBA-MenC	GMT	1
hSBA-MenW-135	GMT	1
hSBA-MenY	GMT	1
Immunogenicity	Ratio of GMT	2
All summaries	% of count, including LL & UL of CI	1
All summaries	% of difference, including LL & UL of CI	2

Abbreviations: CI = confidence interval; GMT = geometric mean titer; hSBA-MenA = serum bactericidal assay against *Neisseria meningitidis* group A using human complement; hSBA-MenC = serum bactericidal assay against *Neisseria meningitidis* group C using human complement; hSBA-MenW-135 = serum bactericidal assay against *Neisseria meningitidis* group W-135 using human complement; hSBA-MenY = serum bactericidal assay against *Neisseria meningitidis* group Y using human complement; LL = lower limit of the confidence interval; rSBA-MenA = serum bactericidal assay against *Neisseria meningitidis* group A using rabbit complement; rSBA-MenW-135 = serum bactericidal assay against *Neisseria meningitidis* group W-135 using rabbit complement; rSBA-MenY = serum bactericidal assay against *Neisseria meningitidis* group Y using rabbit complement; rSBA-MenY = serum bactericidal assay against *Neisseria meningitidis* group Y using rabbit complement; SD = standard deviation; UL = upper limit of the confidence interval.

8.3.1. Methodology for Computing CI

- All CI computed will be two-sided 95% CI.
- The exact 95% CIs for a proportion within a group will be based on the method by Clopper and Pearson [Clopper and Pearson, 1934].
- The standardized asymptotic 95% CI for the group difference in proportions will be based on method 6 described in paper by Newcombe [R Newcombe, 1998].²
- The 95% CI for GMTs will be obtained within each vaccine group separately. The 95% CI for the mean of log-transformed titer will be first obtained assuming that log-transformed values were normally distributed with unknown variance. The 95% CI for the GMTs will be then obtained by exponential transformation of the 95% CI for the mean of log-transformed titer.
- The 95% CIs of the group GMT ratios will be computed using an ANOVA model on the logarithm₁₀ transformation of the titers. The ANOVA model will include the vaccine group as a covariate. Age strata will also be included as a covariate when comparing ACWY>2 to MenPS. In each pairwise comparison, the ANOVA model will use only data from the 2 groups being compared.

MenACWY-TT-100 (C0921004)

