1.2. Rationale for the study and study design

In study MenACWY-TT-027, 613 healthy subjects between 1 and 10 years of age were randomized using a (3:1) ratio to receive either a single dose of MenACWY-TT vaccine or a meningococcal C conjugate vaccine or a meningococcal polysaccharide vaccine. The subjects were followed up for antibody persistence over five years post-vaccination in studies MenACWY-TT-028 through -032. The results showed that subjects vaccinated with MenACWY-TT between ages 1 and 2 years of age had detectable antibodies five years after vaccination in 73.5%, 77.6%, 34.7% and 42.9% of subjects against serogroups A, C, W-135 and Y, respectively. Subjects vaccinated with MenACWY-TT at 2-10 years of age in this same study showed that five years after vaccination 90.8%, 90.8%, 78.6% and 78.6% of subjects had detectable antibodies against A, C, W-135 and Y serogroups, respectively. The main purpose of this study is to continue to evaluate the antibody persistence 6, 7, 8, 9 and 10 years post-administration of MenACWY-TT conjugate vaccine as compared to *Meningitec* or *Mencevax ACWY* when given to healthy subjects 1 to 10 years of age. In addition, the safety and immunogenicity of a booster dose of MenACWY-TT vaccine administered to all eligible subjects 10 years after the primary vaccination will be evaluated.

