10.3. Determination of sample size

The actual sample size of this study with respect to the analysis of persistence and safety and immunogenicity post-booster is determined by a) the sample size of the primary vaccination study MenACWY-TT-027 (108658), b) by assumptions about the enrolment rate at the Year 6-10 extension study, and c) by assumptions about the annual dropout rate. All subjects who were vaccinated in study MenACWY-TT-027 (108658) and received either MenACWY-TT vaccine, *Meningitec* or *Mencevax ACWY* in study MenACWY-TT-027 (108658) will be eligible for this study if they meet the inclusion/exclusion criteria. Six hundred and thirteen subjects (460 in the ACWY-TT group and 75 in the MenCCRM group and 78 in the MenPS group) were enrolled and vaccinated in study MenACWY-TT-027 (108658). An enrollment rate equivalent to approximately 80% of the vaccinated population in study MenACWY-TT-027 (108658) is assumed, and an annual dropout rate of 10%.

If one assumes approximately 10% of subjects dropping out of the persistence study at every visit, then one expects the following numbers of subjects to participate at each persistence time point.

- For the analysis at Year 6, it is estimated that approximately 488 subjects will be enrolled (183 in the ACWY<2, 183 in the ACWY≥2 group, 61 in the MenCCRM group and 61 in the MenPS group)
- For the analysis at Year 7, it is estimated that approximately 440 subjects will be enrolled (165 in the ACWY<2, 165 in the ACWY≥2 group, 55 in the MenCCRM group and 55 in the MenPS group)

C0921004 (MenACWY-TT-100 EXT:027 Y6,7,8,9,10, 200171)
Protocol Amendment 2

- For the analysis at Year 8, it is estimated that approximately 400 subjects will be enrolled (150 in the ACWY<2, 150 in the ACWY≥2 group, 50 in the MenCCRM group and 50 in the MenPS group)
- For the analysis at Year 9, it is estimated that approximately 360 subjects will be enrolled (135 in the ACWY<2, 135 in the ACWY≥2 group, 45 in the MenCCRM group and 45 in the MenPS group)
- For the analysis at Year 10, it is estimated that approximately 326 subjects will be enrolled (122 in the ACWY<2, 122 in the ACWY≥2 group, 41 in the MenCCRM group and 41 in the MenPS group)

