8. STATISTICAL CALCULATIONS

8.1. Derived and Transformed Data

- Age in years will be calculated as (date minus date of birth)/365.25, rounded down to nearest integer.
- Duration from primary vaccination to any persistence time point will use day of primary vaccination as Day 0. Duration from booster will use day of booster vaccination as Day 0.
- Activity date is defined as the date associated with any activity performed at indicated visit.
- For a given subject and a given immunogenicity measurement, missing or non-evaluable measurements will not be replaced. Therefore, an analysis will exclude subjects with missing or non-evaluable measurements.
- The cutoff values for the assays are defined by the laboratory before the analysis and are described in Section 5.7.3 of the protocol.

MenACWY-TT-100 (C0921004)

- A seronegative subject is a subject whose titer is below the cutoff value.
- A seropositive subject is a subject whose titer is greater than or equal to the cutoff value.
- GMTs are calculated by taking the antilog of the mean of the log titer transformations. Antibody titers below the cutoff value of the assay will be given an arbitrary value of half the cutoff value for the purpose of the GMT calculation.
- rSBA vaccine response for groups A, C, W-135, and Y after the booster dose is defined as:
 - For initially seronegative subjects (pre-vaccination titer <1:8): rSBA antibody titers ≥1:32 1 month after vaccination, and
 - For initially seropositive subjects (pre-vaccination titer ≥1:8): a 4-fold increase in rSBA antibody titers 1 month after vaccination.
- hSBA vaccine response for groups A, C, W-135, and Y after the booster dose is defined as:
 - For initially seronegative subjects (pre-vaccination hSBA titer <1:4): hSBA antibody titers ≥1:8 1 month after vaccination, and
 - For initially seropositive subjects (pre-vaccination hSBA titer ≥1:4): a 4-fold increase in hSBA antibody titers 1 month after vaccination.
- For subjects who received MenC vaccine because they were suboptimal responders during the persistence phase of the MenACWY-TT-027 study, all subsequent persistence results for MenC will be replaced by half the cutoff in order to reflect the immunogenicity of the subjects, had they not been revaccinated. This includes Month 126. However, there will be no adjustment to postbooster MenC titers.

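### The GMT-ratio CIs assume one residual variance at about 3:1 group sizes with floored titres; if spread or floored share differs between groups, coverage can miss 95% in either direction.

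*SAP*

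**What the plan says.** SAP 8.3.1 sets the level ("All CI computed will be two-sided 95% CI") and treats GMTs in two ways. For a single group: "The 95% CI for GMTs will be obtained within each vaccine group separately", so each group supplies its own variance. For the ratio: "The 95% CIs of the group GMT ratios will be computed using an ANOVA model on the" log10 scale, with vaccine group as a factor. "In each pairwise comparison, the ANOVA model will use only data from the 2 groups being compared". For one of the two comparisons, "Age strata will also be included as a covariate when comparing ACWY>2 to MenPS"; that term adjusts the mean and leaves a single residual variance. SAP 7.1.2.2 describes the same model. Neither section names a group-specific variance, a Welch interval or a robust standard error, and there is no sensitivity analysis on this point.

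Two other features bear on it:
- **Group sizes.** Protocol 1.2 says that "subjects between 1 and 10 years of age were randomized using a (3:1) ratio". Protocol 10.3 carries the imbalance forward to Year 10: "122 in the ACWY<2, 122 in the ACWY≥2 group, 41 in the MenCCRM group and 41 in the MenPS group".
- **Flooring.** SAP 8.1: "Antibody titers below the cutoff value of the assay will be given an arbitrary value of half the cutoff value". Under the same section, MenC results of subjects revaccinated for a suboptimal response are also set to half the cutoff at every later persistence visit, including Month 126.

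Protocol 10.5.1.2.2 and SAP 7.1.2.2 call the between-group analysis exploratory. Protocol 10.6 calls all analyses descriptive.

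**The concern.** With equal group sizes, a pooled variance gives the right large-sample standard error for a difference in means even if the group variances differ. At 3:1 it does not: the larger group dominates the pooled variance, while the smaller group dominates the true standard error.

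Flooring makes unequal variances plausible, because a group's SD of log10 titre then depends on how many of its values sit at the floor. That share is one of the things the comparison is meant to describe.

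GMTs are part of the primary endpoint. The ratio CI recurs at 5 visits for 4 serogroups (ACWY≥2 versus MenPS) plus MenC (ACWY<2 versus MenCCRM), in 2 assays: 5 × (4 + 1) × 2 = 50 intervals. In a descriptive study the interval is the main statement of uncertainty about each ratio. The group CIs printed beside it would rest on a different variance assumption.

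**Working it through.** **1. Inputs from the documents.** Two-sided 95% CI; two-group ANOVA on log10 titres; rSBA cutoff 1:8, floored to 4. Year 5 detectable antibody after MenACWY-TT (Protocol 1.2, assay not named): 77.6% for MenC at age 1 to <2; 90.8, 90.8, 78.6 and 78.6% for A, C, W-135 and Y at age 2-10.

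**2. The plan's own sizes reproduce.** 0.80 × 613 = 490.4 against 488. From 488, a 10% loss per year gives 439.2, 395.3, 355.8 and 320.2 against the stated 440, 400, 360 and 326. The ratio is 183/61 = 3.00 at Year 6 and 122/41 = 2.98 at Year 10.

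**3. Not in the documents.** Any SD of log10 titre, and any control-group seropositivity. Both are assumed below and varied.

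**4. Large-sample formula.** Let r = control variance / ACWY variance, with 3n and n subjects and ACWY variance 1.
- True variance of the difference: 1/(3n) + r/n = (1 + 3r)/(3n).
- Pooled variance: [(3 + r)/4] × [1/(3n) + 1/n] = (3 + r)/(3n).
- V = true / pooled = (1 + 3r)/(3 + r). Coverage = 2Φ(1.96/√V) − 1. Relative CI width = 1/√V.

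| r | V | Pooled width / correct width | Coverage |
|---|---|---|---|
| 0.25 | 1.75/3.25 = 0.538 | 1.36 | 99.2% |
| 0.5 | 2.5/3.5 = 0.714 | 1.18 | 98.0% |
| 1 | 4/4 = 1 | 1.00 | 95.0% |
| 1.5 | 5.5/4.5 = 1.222 | 0.90 | 92.4% |
| 2 | 7/5 = 1.4 | 0.85 | 90.2% |
| 3 | 10/6 = 1.667 | 0.77 | 87.1% |

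At 1:1, V = 1 for every r.

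**5. Simulation with flooring, n = 122/41, 10,000 runs per cell.** Model A is a floored log-normal (latent SD 1.0 log10). Model B is a responder/non-responder mixture (responders centred 2 log10 above the floor, SD 0.5). The age covariate was not simulated.

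| Model | ACWY vs control seropositive | r | Pooled | Separate variances |
|---|---|---|---|---|
| A | 90.8% vs 10% | 0.08 | 99.7% | 95.0% |
| A | 90.8% vs 50% | 0.52 | 97.7% | 94.8% |
| A | 77.6% vs 50% | 0.61 | 97.4% | 94.9% |
| A | 77.6% vs 77.6% | 1.00 | 95.0% | 94.8% |
| A | 77.6% vs 90% | 1.16 | 93.8% | 94.7% |
| A | 34.7% vs 90% | 2.95 | 86.9% | 94.6% |
| B | 90.8% vs 10% | 0.69 | 96.4% | 92.8% |
| B | 90.8% vs 50% | 2.00 | 89.8% | 94.9% |
| B | 77.6% vs 50% | 1.27 | 93.4% | 95.0% |
| B | 77.6% vs 77.6% | 1.00 | 95.0% | 95.0% |
| B | 77.6% vs 90% | 0.66 | 97.2% | 95.0% |

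**6. Why the direction changes.** In Model B a group's variance is p·0.5² + p(1 − p)·2². At p = 0.908 this is 0.227 + 0.334 = 0.561; at p = 0.5 it is 0.125 + 1 = 1.125; so r = 2.0 and the pooled CI is too narrow. In Model A the same percentages give r = 0.52 and a CI that is too wide. Seropositivity alone does not settle the sign.

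**7. The 92.8% cell.** Here only about 0.10 × 41 = 4 controls lie above the floor, and no variance estimate from so few is dependable. It is the lowest separate-variance value found.

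**The case against.** **Nothing shows that the variances differ.** Correct. A reader might infer that 3:1 sizes and flooring by themselves make the variances unequal, so that these intervals do not have 95% coverage. The documents do not support that. The floored shares or the spreads must also differ, and no SD or control-group figure is given. With equal seropositivity and spread, coverage is 95%.

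**The direction is unknown.** Also correct. A reader might infer that the CI is too wide whenever the control is less seropositive and too narrow whenever it is more so. Step 6 shows this depends on the titre model.

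**The worst figure uses an unlikely input.** Largely so. ACWY<2 is compared with MenCCRM for MenC only, and the protocol's one MenC figure for that group is 77.6%; the 34.7% it reports is for W-135. Later waning or the hSBA could give lower values, but this is assumption. Holding 77.6% under the floored log-normal model, a control at 85% gives 94.4-94.5% and at 95% gives 93.2-93.6%.

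**The comparisons are exploratory.** There is no margin, test or decision, and the group GMT CIs, titre distributions and reverse cumulative curves would reveal unequal spread. This limits the consequence. It does not correct the nominal level printed on the ratio CI.

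What remains: the plan does not say how unequal variances are handled, in a design where pooling is not robust to them.

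**Conclusion.** The point holds conditionally and is a cheap improvement. The ANOVA, the roughly 3:1 sizes and the half-cutoff floor are in the documents; reading ANOVA as a single residual variance is the default interpretation, since the SAP does not use the term pooled.

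Under the assumed models at 122/41, the nominal 95% CI covers about 87% to above 99%. With the ACWY group held at 77.6% or 90.8%, the lowest simulated value is about 90%. Coverage is about 95% when seropositivity and spread are equal. Separate variances give about 94-95% except where very few controls exceed the floor. The size rests on assumed SDs, assumed control seropositivity and two assumed titre models.

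The effect is on the stated precision of the GMT ratios. It does not touch the single-group GMT CIs or any decision rule. A reader might also extend the argument to the longitudinal model in SAP 7.1.3, which fits one covariance matrix across both groups. No calculation here supports a change there, and robust standard errors are a debatable trade under dropout with about 41 controls and up to 12 visits.

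**What to change.** In SAP 7.1.2.2 and 8.3.1, keep the same fixed effects (vaccine group, plus age stratum for ACWY≥2 versus MenPS) and allow a separate residual variance per vaccine group with Satterthwaite degrees of freedom, for example PROC MIXED with REPEATED / GROUP=group and DDFM=SATTERTHWAITE. State this in one sentence in each section and record it in SAP section 10.

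Cost: one extra variance parameter per comparison, and a CI up to about 1% wider if the variances are in fact equal. Because the annual reports are stepwise and cumulative, ratio CIs already reported for earlier visits should be re-run or labelled, so that all years in the final report share one method. Make no change to SAP 7.1.3 on this ground.

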9. CONDUCT OF ANALYSES

9.1. Sequence of Analyses

The persistence analysis will be done in stepwise fashion after the persistence time points for Months 78, 90, 102, and 114 as soon as results are available. The persistence analyses will be performed on as clean as possible data.

The final analysis of immunogenicity, safety, and reactogenicity will be performed on fully cleaned data after the extended safety follow-up (ESFU) time point as soon as results are available for Visit 5, Visit 6, and Visit 7.

The booster analyses will be performed on a validated and frozen database.

The final report containing all persistence, post-booster, and ESFU endpoints will be performed on fully cleaned data.

9.2. Statistical Considerations for Interim Analyses

No statistical adjustment for interim analyses is required.

10. CHANGES FROM PLANNED ANALYSES

Please note that the changes from planned analyses to be included in the clinical study report (CSR) will be identified during the CSR review.

- The adapted ATP cohort and total enrolled cohort have been added and are explained in detail.
- Analysis of persistence for all the antigens MenA, MenC, MenW-135, and MenY will be done using the ATP cohort for persistence at Month X which will include those subjects who received a booster dose of MenC vaccine because they were non-responders after the primary vaccination in Study MenACWY-TT-027. A decision was made to include the results of the subjects who were administered a booster dose of MenC vaccine, since the removal of the results of these subjects from the analysis for persistence of MenC would result in the over estimation of the persistence of MenC.
- The new statement is "who have available assay results for at least 1 of 3 antigens (MenA or MenW-135 or MenY) at Month X." has been modified to "who have available assay results for at least 1 of 3 antigens (MenA or MenW-135 or MenY) or for MenC (for subjects who had not received MenC vaccine because they were non-responders during the persistence phase of Study MenACWY-TT-027 please see Section 7.1 of the SAP) at Month X".

MenACWY-TT-100 (C0921004)

For subjects who received MenC vaccine because they were suboptimal responders during the persistence phase of the MenACWY-TT-027 study, the persistence results for MenC will be replaced by half the cutoff in order to reflect the immunogenicity of the subjects, had they not been revaccinated.

